## SPECIFIC AIMS

There is accumulating evidence that older adults with chronic low back pain (cLBP) have significant lower extremity functional limitations, resulting in difficulty performing necessary daily tasks (i.e., walking, standing, putting on clothing, climbing steps, conducting housework). Moreover, older adults with cLBP suffer from declining lower extremity physical function over time. A recent review by the Centers for Medicare Services reported cLBP as a condition commonly resulting in physical decline among older adults and emphasized the need for interventions to mitigate these effects. Physical Activity (PA) is known to improve functional outcomes among older adults. However, studies to date have not evaluated the effects of PA on physical function among older adults (65+) with cLBP. Therefore, we lack an evidence base for the feasibility and effectiveness of PA interventions in this functionally vulnerable group. Another area of limited investigation among older adults with cLBP is the incorporation of cognitive behavioral therapy for pain (CBT-P) to support and complement a PA program. For example, cognitive restructuring may help patients to modify overly negative thoughts about possible activity-related pain, and activity pacing can be important for helping patients with cLBP learn to plan and structure their PA to avoid pain exacerbations. However, the combination of PA and CBT-P has not been evaluated in older adults with cLBP.

To address these gaps, our proposed study will examine the feasibility and efficacy of home-based PA only and PA + CBT-P programs, compared to a wait-list control group; both programs can be disseminated widely in the VA health care system among older veterans with cLBP. In accordance with general recommendations for PA among patients with LBP, the PA program will be comprehensive, including stretching, strengthening, and aerobic endurance activities. However, the specific types and intensities of the PA will be specifically geared toward older adults. CBT-P will also be based on standard principles but tailored to specific issues for older adults with cLBP, including the challenge of adopting and maintaining a PA program in the context of chronic pain.

Another novel aspect of this project will be the evaluation of baseline pain sensitivity, measured with field-based techniques, as a potential predictor of response to the interventions. Some patients with cLBP have a lower threshold for pain, due to an augmented central pain processing mechanism. As such, measures of pain sensitivity may prove useful in understanding an ongoing refractory pain-process; it is possible that patients who have a lower threshold for pain may respond differentially to behavioral interventions. In particular, these patients may experience greater improvement when CBT-P is offered as an additional program component (compared to PA alone), since these cognitive skills have been shown to influence pain processing. This pilot study will be an important step, ultimately leading to guidance regarding whether some older adults with cLBP should be offered a PA only vs. PA + CBT-P.

To our knowledge this will be the first study to examine the home-based PA only and PA + CBT-P programs among older adults with cLBP, as well as the first to evaluate central pain sensitivity as a predictor of response to these interventions. Therefore preliminary data are needed to support a larger project. Our specific aims are:

**Specific Aim 1:** Examine the feasibility of conducting 12-week home-based, telephone-supported programs of: 1.) PA only and 2.) Combined PA+CBT-P, among older veterans (65+ years) with cLBP. Quantitative measures of feasibility will include the proportions of patients who initiate and complete the programs and adherence to in-home PA recommendations and cognitive behavioral skills practice. We will also collect in-depth qualitative information to assess aspects of the interventions that may need to be modified prior to a larger study.

**Specific Aim 2:** Collect preliminary data to evaluate the efficacy of the PA only and PA + CBT-P programs among older veterans with cLBP. Main outcomes will be an objective test of general physical function (timed up-and-go (TUG)) and self-reported physical function (PROMIS Health Assessment Questionnaire (PROMIS-HAQ)). Secondary outcomes will include: Patient Specific Functional Scale (PSFS), Satisfaction with Physical Function Scale, LBP-specific disability (Roland-Morris Low Back Pain and Disability Questionnaire (R-MDQ)), and the Coping Strategies Questionnaire.

**Specific Aim 3:** Examine whether baseline distal Pressure-Pain Threshold, an established biological marker of pain sensitization, and the Central Sensitivity Inventory, which measures health-related symptoms common to central pain sensitization, predict differential response to the PA only and / or PA + CBT-P programs among older veterans with cLBP.

There is a need to develop and disseminate effective programs to improve PA and ultimately physical function in this patient subgroup. This project will be a key first step in evaluating a home-based PA and PA + CBT-P programs that could be widely disseminated in the VA at relatively low cost and reach many functionally vulnerable older veterans with cLBP.

## BACKGROUND AND SIGNIFICANCE

### Low Back Pain is Highly Prevalent in Veterans and Older Adults

[figure not shown]
Low back pain (LBP) is a complex and a multidimensional condition resulting in approximately \$100-\$200 billion per year in costs for the U.S. LBP is the second most common cause of disability and a common reason to seek primary care. LBP is particularly common among U.S. veterans. Sixty-percent of VA primary care patients report having chronic pain that significantly impacts self-rated health, functional status and self-reported quality of healthcare; of these, about 60% specifically report having LBP. Similar to the civilian population the prevalence of chronic low back pain (cLBP), defined as pain lasting >3 months, is rising steadily among veterans, with a 4.8% annual increase from 2000-2007; this rate of increase is higher than those for diabetes, hypertension and depression. Among older adults, LBP is also very common, with prevalence estimates in the general community ranging from 13 to 49%. The wide range is likely due to methodological differences in the definition of LBP and age range of included participants. Research on interventions to treat cLBP in older adults has been very limited. This is an important consideration as the proportion of people over 65 years of age is expected to increase over the next 25 years, and the prevalence of musculoskeletal problems is expected to increase as well.

### Older Adults with cLBP are Particularly Susceptible to Functional Decline

A number of studies have shown that cLBP is associated with functional limitations and decline among older adults, independent of other health conditions. Among older adults in the Health ABC study, for example, functional capacity scores worsened with increasing frequency and intensity of LBP. Edmond and Felson found that among older adults in the Framingham Heart Study, 18% to 34% of all functional limitations were attributable to back symptoms. In terms of ongoing functional decline, Reid and colleagues found that participants with 4 months of LBP at baseline had declining gait speed, chair stands and foot tapping over the subsequent 18 months. The impact of LBP on physical function in older adults is particularly important because functional decline is associated with many deleterious effects, including changes in cognitive function and mortality. **We have chosen to focus on physical function as a primary outcome since LBP does not have to be completely eliminated to avoid adverse consequences of functional decline.**

### Physical Activity Can Improve Functional Outcomes, But Older Adults with cLBP Are Understudied

The relationship between cLBP and physical function is primarily based upon a model where cLBP leads to decreased PA, subsequent deconditioning and neuromuscular changes, followed by decreased physical function (See Figure).

### Cognitive Behavioral Therapy Can Improve Pain Perception for cLBP

Cognitive behavioral therapy comprises techniques that aim to influence maladaptive emotions, behaviors and cognitions through a goal-oriented, systematic procedure. Cognitive behavioral approaches have been applied to many health conditions and health behaviors and can be flexibly adapted to a wide range clinical settings, including telemedicine. Cognitive behavioral therapy for pain (CBT-P) is associated with improved outcomes among individuals with cLBP, as well as other pain-related conditions. Previous studies also show that older adults are willing to engage in self-management programs for pain that include both cognitive and PA components. There is growing evidence that CBT-P alone or combined with PA can improve pain and function. However, the effectiveness of PA + CBT-P compared to PA alone has not been evaluated among older adults with cLBP.

### Central Pain Sensitivity May Predict Differential Response to PA for Low Back Pain

To date it has been challenging to understand why some individuals with cLBP respond favorably to evidence based interventions, such as PA, and others do not. One factor that may underlie this differential treatment response is central pain sensitivity. Findings from cLBP studies suggest that some patients have an augmented pain sensitivity, in which the pain experience results from or is exacerbated by abnormal pain processing rather than damaged or inflamed peripheral structures. As such, pain sensitivity may prove useful in understanding an ongoing refractory pain-process and particularly why some patients do not respond to a PA intervention alone. There is evidence that psychosocial characteristics such as pain catastrophizing and depression contribute to pain sensitization, and CBT-P can improve these psychological processes and outcomes. Therefore older adults with cLBP who have higher baseline pain sensitivity may respond better when PA is combined with CBT-P versus a PA program alone. However, this has not been investigated, and this pilot study will be an important step in this area of research.

### Summary of the Significance of the Proposed Study

Although there have been other studies of PA for patients with cLBP, including a walking program among veterans, our study makes novel and significant contributions: 1.) It will be specific to older adults, who are more susceptible to comorbid conditions and functional deficits, whereas previous studies have been conducted primarily among middle-aged samples. 2.) It will incorporate a combination of stretching, strengthening, and aerobic activity in a semi-structured approach, conducted primarily in the home environment; these types of physical activity programs have been effective for improving functional status among older adults in general, and they can be disseminated widely in the VA healthcare system. 3.) It will compare the effectiveness of PA + CBT-P vs. PA alone, which has not been investigated among older adults with cLBP. 4.) It will evaluate the potential role of central pain processing as a predictor of response to the PA alone and PA+CBT-P interventions, which has implications for downstream tailoring of care for patients.

## RESEARCH DESIGN AND METHODS

**Study Design:** This project will be a randomized controlled pilot trial of 12-week programs of PA only and PA + CBT-P, both supported by telephone, among 60 older adults with cLBP at the Durham VA Medical Center (VAMC). Participants will be randomly assigned with equal allocation to the two intervention groups or a wait-list control (WL) group. Participants will complete assessments at baseline, then approximately 12-weeks later. Participants in the WL group may choose to participate in the PA only or PA + CBT-P program following 12-week assessments. The 12-week follow-up was chosen because this is a reasonable time frame for older adults to experience neuromuscular adaptations and changes in general physical function. We chose a home-based exercise program because of its feasibility for widespread dissemination in the VA and because prior work has shown that home-based PA programs are safe and effective for improving physical function among older adults. We have chosen telephone-based approach because we expect this method of communication will be well received by older veterans, based on our prior and ongoing work in telephone-based PA support for osteoarthritis. We have chosen to include a control group in this pilot trial to account for any general improvement or changes in primary care intervention that may be observed in the course of cLBP. Participants will be paid \$30 for each assessment visit for time and travel.

**Participants and Recruitment:** The target sample for this study will include older veterans (65+ years) with cLBP at the Durham VAMC. We may over-sample women to ensure this important demographic group of Veterans is adequately represented in the study. In particular, we may prioritize contacting women Veterans who meet study entry criteria so that they comprise at least 30% of the study sample. We will have three recruitment mechanisms:

1. Using VistA, we will first identify potential participants, age 65+ who have an ICD-9 code for low back pain or an indication of low back pain on the problem list and no exclusionary diagnoses. Because the study involves two in-person sessions, we may restrict this data pull to patients who live relatively close to the Durham VAMC. For example, we may initially restrict mileage to 60 miles from the Durham VAMC and based on our experience with this radius, we may expand or narrow this mileage. Next, we will review electronic medical records to confirm a physician diagnosis of chronic low back pain and further assess exclusion criteria. We will then mail introductory letters to these patients, providing a brief description of the study and informing patients that a study team member will be calling them to assess their eligibility and interest in participating. The letter will also include a telephone number patients may call if they are not interested in participating and do not wish to receive a follow-up call.

During the telephone call, a study team member will administer a screening questionnaire to assess additional eligibility criteria, including verification of cLBP symptoms. If veterans meet screening criteria and are interested in participating in the study, they will be asked to meet the Research Assistant at the VAMC for a baseline study visit.

2. We will work with Hospital Informatics to set up the CPRS consult option for referral of potential research participants into this study. We will provide information to health care providers in ambulatory care, geriatric services ([name] is Director of the Geriatrics Clinic), and other services as necessary, to inform them about the study and availability of the consult. This may include information distributed by email, flyers, and in-person visits to clinic team meetings. We will designate two study team members to receive the consult as a View Alert. These staff will review the electronic medical record to assess whether the patient is eligible. If the patient is eligible based on medical record review, an introductory letter will be mailed, and the remaining screening and baseline appointment scheduling procedures will follow those described above. The staff will

then respond to the provider who issued the consult to let them know if the patient is eligible and will / will not be contacted for further screening procedures. We have successfully utilized these strategies in other research projects.

3. We will create a brochure that includes the study description and contact numbers for the project coordinator and research assistant. We will provide the brochure to physical therapists and potentially other providers at the Durham VAMC so that they can place them in clinic areas where they can be visible to veterans. If a veteran is interested and calls the study team, we will review the medical record to see if the veteran is eligible. If eligible by medical record review, the veteran will be screened using the same telephone screening method explained in the other recruitment methods listed previously.

The baseline visit will include administration of consent, baseline questionnaires and functional assessments, and an examination by a physical therapist ([name]). During the physical therapist exam a Well Straight Leg Raise physical examination test will be used to determine the presence of ongoing sciatica, which may be exacerbated with physical activity. This test is conducted with the participant in supine position and the examiner supporting the non-involved leg. The examiner then raises the leg. A positive test is indicated if the participant reports concordant leg pain. This test is commonly used in clinical practice and is highly specific for sciatica (specificity=97%). Results of the physical therapist examination will be used to determine physical appropriateness for participation in the home-based PA program, based on the clinical expertise of the physical therapist and the criteria described below. If the physical therapist determines that the patient is not appropriate for participation in a home exercise program, the patient's primary care provider will be notified via response to the consult if the patient was referred by the provider, and that provider may refer the patient for more supervised physical therapy. All other non-qualified patients will have a progress note entered into CPRS stating that they may benefit from supervised physical therapy. During the baseline visit the participants will also receive a packet with several self-administered measures to fill out either at that time, or they can complete the questionnaires at home and then mail them back to the study team using a pre-addressed stamped envelope. We will monitor the return of these items and may need to do telephone follow-up calls to ensure that all measures are returned.

**Randomization:** Following the completion of all baseline assessments and the physical therapist examination, participants will be randomly assigned to one of the two intervention arms or to the wait list control group via an envelope selection procedure or by use of a randomization table programmed into the study tracking database. Randomization will be stratified by Central Sensitization Inventory (CSI) score (described below under Measures of Central Pain Sensitization), categorized by >40 vs. ≤40; this to ensure individuals with high vs. low pain sensitivity will be equally distributed across study groups.

The principal investigator, project coordinator, or physical therapist will select an envelope from one of two batches. One batch of envelopes will be for participants who have a CSI score of >40. The other batch of envelopes will be for those with CSI ≤40. Following randomization, participants assigned to the PA or PA + CBT-P intervention will receive their first intervention visit from the physical therapist, unless they need to complete this at another time for scheduling reasons.

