**Inclusion / Exclusion Criteria:** Based on previous studies, we will **include participants who:**

- 1) Self-report having had lower back pain on most days for greater than three months.
- 3) Can complete a 10 second semi-tandem stand and walk 8' in 6.0 seconds.
- 4) Report they are not satisfied with their current state of functional ability, based on reporting "dissatisfied" with at least one aspect of physical function on the Satisfaction with Physical Function Scale.
- 5) Can safely participate in the intervention based upon the physical therapist baseline examination and clinical expertise.

Veterans will be **excluded if they have:**

- 1) acute unilateral or bilateral sciatica (based on Physical Therapist exam at baseline); isolated coccyx pain (based on self-report at screener);
- 2) dementia or other significant cognitive impairment;
- 3) movement or motor neuron disorders (e.g., Parkinson's Disease, Multiple Sclerosis, Amyotrophic Lateral Sclerosis);
- 4) rheumatoid arthritis, fibromyalgia, or other systemic rheumatic disease;

- 5) hospitalization for a stroke, myocardial infarction, heart failure, or coronary artery revascularization in the past 3 months;
- 6) significant hearing impairment (must be able to talk on the telephone);
- 7) psychosis or current, uncontrolled substance abuse disorder;
- 8) legally blind;
- 9) any other health conditions determined by the study team to be contraindications to performing mild to moderate home exercises.

Based on our prior and ongoing studies at the Durham VAMC that have similar recruitment and procedural methods, we are confident we can enroll n=60 older veterans with cLBP within the proposed recruitment period for this study. Study participants excluded after consent due to the presence of sciatica or other functional limitations or health problems as determined by the physical therapist at baseline will not be randomized and thus not included in our total enrollment goal, i.e. we plan to consent enough participants such that a total of n=60 are eligible to participate, having met the eligibility criteria assessed following consent.

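### Staff, including the therapist who settles eligibility, may pick allocation envelopes, with no concealment or within-stratum restriction described, so allocation is open to steering and CSI balance is not ensured

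*Combined protocol and SAP*

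**What the plan says.** All statements are in the combined protocol and SAP, under Research Design and Methods.

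- **Study Design** sets a total of 60 and the ratio: "Participants will be randomly assigned with equal allocation to the two intervention groups or a wait-list control (WL) group". That implies 20 per arm.
- **Randomization** leaves the mechanism open. Assignment is "via an envelope selection procedure or by use of a randomization table programmed into the study tracking database". It follows the baseline assessments and the therapist's examination.
- **Randomization** stratifies by CSI, "categorized by >40 vs. ≤40", and gives the purpose: "this to ensure individuals with high vs. low pain sensitivity will be equally distributed across study groups".
- For the envelope route: "The principal investigator, project coordinator, or physical therapist will select an envelope from one of two batches". There is one batch per CSI stratum. The therapist then gives participants in the two active arms their first intervention visit, normally straight after randomization.
- **Inclusion / Exclusion Criteria**, criterion 5, makes eligibility depend on the therapist's judgement: "Can safely participate in the intervention based upon the physical therapist baseline examination and clinical expertise".
- **Analyses** uses the CSI cutpoint of 40 again, in a group-by-CSI interaction for Aim 3.

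The text does not say whether envelopes are sealed, opaque, numbered or taken in order. It does not say how many envelopes per arm each batch holds, who prepares or keeps them, or how the sequence is generated. For the database table it gives no blocking and no rule on who can view upcoming assignments.

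**The concern.** Two separate matters are at stake.

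**Selection.** One person may judge whether a participant is fit for a home exercise programme, select that participant's allocation from a batch, and then deliver the treatment. Concealment exists to break that chain, and no safeguard is described. If assignment were influenced by the therapist's impression, the arms could differ in prognosis before treatment starts. The planned ANCOVA adjusts for the measured baseline score, not for whatever else the therapist saw in the examination. The Analyses section says the study will concentrate on effect sizes and use its data to size a larger trial, so a shifted effect estimate would damage the pilot's main product.

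**Balance.** Stratifying means keeping separate lists or batches. It produces equal numbers within strata only if the sequence inside each stratum is restricted, for example by permuted blocks. The plan says stratification will ensure equal distribution but describes no such restriction.

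**Working it through.** **Inputs from the protocol:** N = 60, three arms, equal allocation, two CSI strata. The only plan figure to reproduce is 60/3 = 20 per arm. The protocol gives no power calculation.

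**Assumptions, because the protocol gives no value:** the number with CSI above 40 (base case 20 of 60; range 12 to 30), and the number of envelopes per arm in each batch (7 to 20).

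**Step 1. Balance in the high-CSI stratum, 20 participants.** The gap is the largest minus the smallest arm count. Unrestricted draws follow a multinomial (20; 1/3, 1/3, 1/3). Draws without replacement from a batch with m envelopes per arm follow a multivariate hypergeometric. Simulation with 400,000 replicates gives:

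| Procedure | P(gap of 4 or more) |
|---|---|
| Unrestricted | 61% |
| Batch, m = 20 | 48% |
| Batch, m = 15 | 42% |
| Batch, m = 10 | 23% |
| Batch, m = 8 | 2% |
| Batch, m = 7 | 0% |

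The last row is exact. Drawing 20 of 21 envelopes leaves one behind, so the arms differ by at most 1. A batch behaves as one large block and balances only when nearly used up.

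**Step 2. Varying the CSI share.** For 12, 18, 24 and 30 high-CSI participants, unrestricted draws give 42%, 56%, 65% and 70%. A batch with m = 20 gives 35%, 44%, 49% and 50%.

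**Step 3. Total arm sizes.** Under unrestricted assignment of 60, P(exactly 20/20/20) = 60!/(20!)³/3⁶⁰ = 1.4%, and the smallest arm has 16 or fewer in 49% of trials. With batches of 20 per arm in each stratum and a 20/40 CSI split, the 49% falls to 23%.

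**Step 4. What imbalance costs.** The standard error of a two-arm difference is proportional to √(1/n₁ + 1/n₂). Relative to 20 and 20, unrestricted assignment raises it by a median of 1% (90th percentile 9%). For the group-by-CSI contrast it is proportional to the square root of the sum of four reciprocal cell counts. Relative to exact balance with 20/40 strata, the median rise is 3% (90th percentile 16%).

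**Step 5. What steering could cost (illustration only).** If k of 20 participants in an arm are replaced by people whose prognosis is d SD better, the arm mean shifts by (k/20) × d. With k = 3 and d = 1, that is 0.15 SD; with k = 1 and d = 0.5, it is 0.025 SD. The standard error of a two-arm difference, √((2/20)(1 − r²)), is 0.32 SD at r = 0 and 0.23 SD at r = 0.7, where r is the baseline–follow-up correlation. The protocol gives no value for k, d or r.

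**Step 6. Under blocking.** Within a stratum, an unfinished block of 3 leaves a gap of at most 1 and an unfinished block of 6 at most 2. With sizes 3 and 6 mixed, the gap is at most 2 per stratum and 2 + 2 = 4 overall.

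**The case against.** The strongest reply is that much of this rests on silence. The protocol does not say that envelopes are unsealed or that blocking is absent. A reader might infer that there is no blocking, or that staff can see the next assignment; the documents support neither, only that no blocking and no concealment are described. The therapist is one of three permitted selectors, and nothing suggests that anyone would misuse the role. A reader might also picture the eligibility judgement as coming minutes before the draw. The protocol does not say so, and because some baseline questionnaires may be mailed back, the interval may be longer. These limits are accepted. The overlap of roles is nevertheless a written rule, not a silence.

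A second reply is that the database table already solves the problem. It is permitted, but it is not described as concealed or blocked, and an unblocked table would leave the same imbalance.

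A third is that the balance figures depend on batch size. That is right: the result runs from 0% to 48% for finite batches, and the 61% applies only to unrestricted draws. The precision cost is also modest, as step 4 shows, so a reader should not infer that imbalance would seriously damage Aim 3.

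Finally, the steering scenario is hypothetical, and its 0.15 SD lies below the standard error. That also stands. It shows a scale and is not an estimate.

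**Conclusion.** The point holds in a limited form. As written, the plan permits the person who settles eligibility and starts treatment to select the allocation, and it describes no concealment or within-stratum restriction for either mechanism. That is an opportunity for selection bias, whose size the documents cannot determine. Stratifying by CSI does not by itself ensure the stated equal distribution or the equal allocation. With 20 high-CSI participants assumed, the chance of a gap of 4 or more is about 61% with unrestricted draws and 48%, 23% or 0% with 20, 10 or 7 envelopes per arm. Because the loss of precision is modest, selection bias is the main reason to act and balance is secondary. The change is cheap and should be made; confidence is high on the text and lower on any single magnitude.

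**What to change.** - Commit to one mechanism, preferably the table in the tracking database that the plan already permits.
- Specify a computer-generated sequence in permuted blocks of randomly varied size (for example 3 and 6) within each CSI stratum, prepared by someone who does not enrol participants. Hide both the sequence and the block sizes from enrolling staff.
- Release each assignment only after the therapist's eligibility decision and the baseline measures are recorded. The order of events is already in the plan; the new element is making release conditional on the record.
- Remove the physical therapist from those who may obtain the assignment.
- If envelopes are kept as a backup, make them sealed, opaque and sequentially numbered, fill them from the same blocked sequence, and take them strictly in order.

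The cost is a wording change and minor programming. The downside is some predictability: at a single site where the therapist delivers both active arms and so learns the assignments, small blocks can sometimes be guessed. Varying and concealing the block size limits this but does not remove it.
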